### **3.3. Benefit/Risk Assessment**

#### **3.3.1. Risk assessment for Relvar/Breo 100/25mcg and 200/25mcg**

For Relvar/Breo ELLIPTA, the following risks and the corresponding mitigation strategies, as applicable to asthma patients, were taken from the summary of safety concerns in the European Union – Risk Management Plan (EU-RMP Version 10). For Relvar/Breo the rationale for the risk assessment was derived from the 2014-2016 Investigator Brochures, from an integrated analysis of key Relvar/Breo studies.

Potential Risk of Clinical Significance	Summary of Data/Rationale for Risk	Mitigation Strategy
Investigational Product (IP) (fluticasone furoate [FF]/vilanterol [VI])		
Pneumonia in patients with asthma	
In an integrated analysis of 11 studies in asthma (7034 patients), the incidence of pneumonia (adjusted for exposure, due to low numbers and limited number of patients on placebo) seen with FF/VI 100/25 microgram strength (9.6/1000 patient years) was similar to placebo (8.0/1000 patient years). The incidence was slightly higher for FF/VI 200/25 microgram (18.4/1000 patient years). No risk factors were identified.
 
In HZA115150 (SLS Asthma) the number of subjects who experienced a Pneumonia SAESI was low. In total, 23 subjects (1%) randomised to initiate treatment with FF/VI arm experienced 24 Pneumonia SAESIs, and 16 subjects (<1%) randomised to continue usual care experienced 18 Pneumonia SAESIs.
 
The incidence rate of subjects experiencing a Pneumonia SAESI per 1000 subject-years at risk by randomised treatment arm, was 10.36 in the FF/VI arm and 7.14 in the usual care arm. The number of Pneumonia SAESIs per 1000 subject-years at risk by randomised treatment arm was 10.81 in the FF/VI arm and 8.03 in the usual care arm.
 
The incidence ratio for Pneumonia SAESIs for subjects randomised to initiate treatment with FF/VI versus those randomised to continue usual care was 1.4 (95% CI: 0.8, 2.7). The upper limit of the 95% CI was
	
The risk of pneumonia in asthma patients is consistent with the risk of other ICS. Subjects are not at an increased risk in this study, since they enter the study on an existing ICS treatment. Subjects are alerted to the potential risk of pneumonia in the informed consent.
 
Subjects with a concurrent respiratory disease are excluded from the study.

Potential Risk of Clinical Significance	Summary of Data/Rationale for Risk	Mitigation Strategy
	
higher than the pre-specified non-inferiority margin of 2; therefore, being randomised to initiate treatment with FF/VI was not shown to be non-inferior to being randomised to continue usual care with regards to the incidence of Pneumonia SAESIs.
	
Serious cardiovascular events	
In an analysis performed on the 18 key studies in subjects with asthma, eight serious cardiovascular events have been reported in patients exposed to FF/VI. Seven events in FF/VI 100/25 and one event in FF/VI 200/25. This represents an incidence less than 1% in the asthmatic patients exposed to FF/VI.a
 
The events reported include atrial fibrillation, acute coronary syndrome, coronary artery disease, hypertension, myocardial ischemia, tachyarrhythmia and tachycardia.
 
Therefore, fluticasone furoate/vilanterol should be used with caution in patients with severe cardiovascular disease or heart rhythm abnormalities, thyrotoxicosis, uncorrected hypokalaemia or patients predisposed to low levels of serum potassium.
	
Subjects with existing serious cardiovascular disease, thyrotoxicosis, uncorrected hypokalaemia or patients predisposed to low levels of serum potassium are excluded from the study.
 
Investigators are made aware of the potential class effects of LABAs and are advised to exercise caution for subjects with existing serious cardiovascular disease (Section 6.3 [Warnings and Precautions] of the IB).

Decreased bone mineral density and associated fractures	
Risk of fracture has been associated with oral corticosteroids. It is unclear if inhaled corticosteroids carry the same risk.
 
Currently the risk of reduced bone mineral density has not been observed in the asthma population [Jones, 2002]. In addition specific assessments in adolescents with asthma have not demonstrated an
	
Subjects will be informed about the risk of decreased bone mineral density and bone fractures in the informed consent.
 
Investigators are made aware of the potential for this ICS class effect. Subjects will be advised to seek medical treatment if any signs of decreased bone mineral density or fractures occur.

Potential Risk of Clinical Significance	Summary of Data/Rationale for Risk	Mitigation Strategy
	
effect on bone mineral density, when controlled for growth [König, 1993; Turpeinen, 2010].
 
In an analysis performed on the 11 key studies in subjects with asthma bone fractures were reported by <1% (7034 patients) of subjects who received FF/VI 100/25 and was usually associated with trauma
	
All subjects will already be prescribed ICS/LABA treatments for their asthma. Therefore, it is unlikely that such an effect will occur.

Corticosteroid associated eye disorders	
This is considered a class effect of ICS. Preclinical studies showed FF at high dose comparable to other high dose corticosteroids. In study HZA106839 (FF/VI, FF and FP in subjects with asthma), formal ophthalmic assessments were conducted (including lens opacities classification system [LOCS] III evaluations for ocular opacities) throughout the study. This study showed no apparent effects on lens opacification, compared to baseline. During studies in both subjects with asthma and COPD, no associated affect on ocular disorders was observed.
	
Subjects will be informed about the risk of corticosteroid associated eye disorders in the informed consent. They will be advised to seek medical treatment if any signs of eye disorder occur. Investigators are made aware of the potential for this class effect in Section 5.3.3.7 (Ophthalmic Effects) of the IB.
 
All subjects will already be prescribed ICS/LABA treatments for their asthma. Therefore, it is unlikely that such an effect will be experienced.

Paradoxical bronchospasm may occur with an immediate increase in wheezing after dosing.		
First dose of Relvar/Breo will be administered at the clinical site under supervision Paradoxical bronchospasm should be treated immediately with a short-acting inhaled bronchodilator. Relvar/Breo ELLIPTA should be discontinued Immediately. The subject would be withdrawn from study.

a. RELVAR studies summarized include FFA109684, FFA109685, FFA109687, B2C109575, HZA106827, HZA106829, HZA113091, HZA113714, HZA113719, HZA116863, HZA106837, HZA106839, HZA106851, FFA112059, FFA114496, FFA115283, FFA115285, B2C112060.

More detailed information about the known and expected benefits and risks and reasonably expected adverse events of Relvar/Breo may be found in the Investigator's

Brochure, Development Safety Update Report or Summary of Product Characteristics Benefit Assessment.

As a result of switching from other prescribed ICS/LABA combination products and being randomised to a treatment arm in the study, subjects may switch from an inhaled therapy that is taken twice daily, to a once daily therapy (Relvar/Breo) the patients in this study may have better adherence and so possibly better asthma control. There is also a potential benefit from use of the CIS. This has the potential to increase their adherence through interaction with the data outputs and engagement with their asthma. Data with marketed products suggests that adherence improves with less frequent administration/simplification of therapy and therefore it is expected that a once-daily treatment could improve adherence, which may lead to improvements in disease control and reductions in healthcare resource utilisation costs [Foster, 2014, Price, 2010, Toy, 2011].

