### **Screening Visit (V1)**

Subjects who have provided their informed consent will be screened at Visit 1 (V1) for inclusion on the study. Subjects who meet all the inclusion criteria, including an ACT of <20, will enter the flexible run-in period. Screening and starting the flexible run-in can occur at the same visit, however for logistical reasons the flexible run-in can start at a separate visit, which must be within 7 days of the screening visit and the subject's inclusion on the study. Should a subject not meet the inclusion/exclusion criteria, they will be registered as a screen failure.

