## 6.2. Exclusion Criteria

A subject will not be eligible for inclusion in this study if any of the following criteria apply:

RELEVANT HABITS
1. Subjects with a known or suspected alcohol or drug abuse which in the opinion of the investigator could interfere with the subject's proper completion of the protocol requirement
CONTRAINdications
2. History of life threatening asthma: Defined for this protocol as an asthma episode that required intubation and/or was associated with hypercapnea, respiratory arrest or hypoxic seizures within the last 6 months 3. A lower respiratory tract infection within 7 days of the screening visit. 4. Concurrent diagnosis of COPD or other respiratory disorders including active tuberculosis, lung cancer, bronchiectasis, sarcoidosis, lung fibrosis, pulmonary hypertension, interstitial lung diseases or other active pulmonary diseases. 5. History of hypersensitivity/intolerance to any components of the study inhalers (e.g., lactose, magnesium stearate). In addition, subjects with a history of severe milk protein allergy that, in the opinion of the study physician, contraindicates participation will also be excluded. 6. Historical or current evidence of clinically significant or rapidly progressing or unstable cardiovascular, neurological, cardiovascular, neurological, renal, hepatic, immunological, endocrine (including uncontrolled diabetes or thyroid disease) or hematological abnormalities that are uncontrolled. Significant is defined as any disease that, in the opinion of the investigator, would put the safety of the subject at risk through participation, or which would affect the analysis if the disease/condition exacerbated during the study.
DIAGNOSTIC ASSESSMENTS AND OTHER CRITERIA
7. Patient who have ever received treatment with biological based therapy e.g. omalizumab, mepolizumab, for asthma 8. Subjects who have received an investigational drug and/or medical device within 30 days of entry into this study (Screening), or within five drug half-lives of the investigational drug, whichever is longer 9. A subject will not be eligible for this study if he/she is an immediate family member of the participating investigator, sub-investigator, study coordinator, employee of the participating investigator, or any family member of a Propeller Health employee

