## **7.9. Concomitant Therapy**

All medications for asthma, excluding biological therapy and for other disorders that are not contra indicated in asthma, or prohibited in this study, may be continued throughout the study.

Please consult the prescribing information for the full list of medications which need to be used with caution:

Beta-blockers: Use with caution. May block bronchodilatory effects of beta-agonists and produce severe bronchospasm.

Diuretics: Use with caution. Electrocardiographic changes and/or hypokalemia associated with non-potassium-sparing diuretics may worsen with concomitant beta-agonists.

Non-study asthma medications: A detailed history of previous 3 months and up to 12 months prior to inclusion, as available, for prescriptions for maintenance medications (ICS/LABA combination) will be captured in the subjects eCRF and also any other ongoing asthma medications at inclusion.

Any medication or vaccine of relevance to the study or prescribed for safety events, including exacerbations experienced during the study, that the subject is receiving at the time of enrolment or receives during the study must be recorded in the eCRF in addition to medical records. As minimum the following will be needed:

- reason for use
- dates of administration including start and end dates

- dosage information including dose and frequency

Over-the-counter medicines, vitamins, and/or herbal supplements are not required to be captured.

The Medical Monitor should be contacted if there are any questions regarding concomitant or prior therapy.

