### **8.1.1. Liver Chemistry Stopping Criteria**

There are no scheduled blood tests in this study. If however, the subject has a routine blood test during the study and the results suggest abnormal liver function, then the liver stopping criteria will apply.

**Liver chemistry stopping and increased monitoring criteria** have been designed to assure subject safety and evaluate liver event etiology (in alignment with the FDA premarketing clinical liver safety guidance). These protocol guidelines are in alignment with FDA premarketing clinical liver safety guidance:

<http://www.fda.gov/downloads/Drugs/GuidanceComplianceRegulatoryInformation/Guidances/UCM174090.pdf>.

Discontinuation of study treatment for abnormal liver tests should be considered by the investigator when a subject meets one of the conditions outlined in the algorithm, see [Appendix 5](#), or if the investigator believes that it is in the best interest of the subject.

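### Protocol Section 3.3.1 says patients with uncorrected hypokalaemia, or prone to low potassium, are excluded, but no criterion in Section 6.2 applies this

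*Protocol*

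**What the plan says.** In the current protocol (Amendment 01), the Section 3.3.1 table pairs each risk of FF/VI with a mitigation. In the row on serious cardiovascular events, the mitigation is that certain patients are kept out, and two of the groups concern potassium: "uncorrected hypokalaemia or patients predisposed to low levels of serum potassium are excluded from the study". The pneumonia row makes the same kind of statement: "Subjects with a concurrent respiratory disease are excluded from the study".

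Section 6.2 lists nine exclusion criteria. Exclusion 4 takes up the pneumonia row ("Concurrent diagnosis of COPD or other respiratory disorders including active tuberculosis"). The criterion nearest to the potassium groups is exclusion 6. It covers significant or unstable disease in a fixed list of organ systems: cardiovascular and neurological, then "renal, hepatic, immunological, endocrine (including uncontrolled diabetes or thyroid disease) or hematological abnormalities that are uncontrolled". A disease counts as significant if it, "in the opinion of the investigator, would put the safety of the subject at risk through participation", or if its worsening would affect the analysis.

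Section 5.1 (Screening Visit) sets the operative rule: "Should a subject not meet the inclusion/exclusion criteria, they will be registered as a screen failure". Section 7.9 allows diuretics with caution and warns that "hypokalemia associated with non-potassium-sparing diuretics may worsen with concomitant beta-agonists". Section 8.1.1 adds: "There are no scheduled blood tests in this study". Section 8.1.2 says no ECG is planned.

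**The concern.** Anyone reading Section 3.3.1, including an ethics committee, would take the potassium exclusion to be in force, and the benefit/risk conclusion in Section 3.3.2 leans on such measures. Sites, however, enrol on Section 6. If the exclusion is missing there, a patient with known uncorrected hypokalaemia from a cause outside exclusion 6 could be enrolled in full compliance with the criteria, although Section 3.3.1 lists that patient as kept out. Every participant takes vilanterol, a LABA, with salbutamol as needed, and Section 7.9 itself recognises that beta-agonists can worsen diuretic-related low potassium.

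There is also a reporting side. SAP Section 4.1 bases its summary of eligibility deviations on the inclusion/exclusion page of the eCRF. If that page mirrors Section 6, which is an assumption, such an enrolment would not appear in that summary.

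**Working it through.** No arithmetic beyond a count applies. The check sets each exclusion stated in Section 3.3.1 against the criteria, using one standard throughout: does a criterion in Section 6.2 name the condition or its disease class?

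| Group stated as excluded in 3.3.1 | Row | Named in 6.2 by condition or class? |
|---|---|---|
| Concurrent respiratory disease | Pneumonia | Yes, exclusion 4 |
| Serious cardiovascular disease | Cardiovascular events | Yes, exclusion 6 (cardiovascular) |
| Thyrotoxicosis | Cardiovascular events | Yes, exclusion 6 (thyroid disease) |
| Uncorrected hypokalaemia | Cardiovascular events | No |
| Predisposition to low potassium | Cardiovascular events | No |

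The table in 3.3.1 has five risk rows: pneumonia, cardiovascular events, bone density, eye disorders and paradoxical bronchospasm. Two of them state an exclusion. Groups stated as excluded: 1 + 4 = 5. Carried into 6.2: 3. Not carried: 5 − 3 = 2.

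**What exclusion 6 reaches.** Its definition of significant qualifies a closed list of organ systems whose abnormalities must be uncontrolled; it is not a free-standing catch-all. It can reach low potassium caused by uncontrolled renal or endocrine disease, if the investigator judges it significant. It does not clearly reach hypokalaemia caused by a diuretic. Nor does it fit a patient who is only predisposed, with nothing currently uncontrolled.

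**Other places that might supply the exclusion.**
- Section 6.1 has no potassium item.
- The randomisation criterion is the ACT score only.
- The prohibited medications in Section 7.10 do not include diuretics.
- Section 7.9 handles diuretics by caution. This conflicts with the stated exclusion only if diuretic users count as predisposed, and the protocol does not define that term.

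**Remaining safeguards.**
- Medical history and physical examination at Visit 1.
- Use of suitable routine results obtained before consent (Section 9).
- Recording of clinically significant local laboratory values (Section 9.4.3).
- QTc stopping rules if an ECG happens to be done (Section 8.1.2).
- The cautions in Section 7.9.

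Each may lower the risk. None of them applies the stated exclusion, and with no scheduled blood test or ECG the protocol has no planned way to detect low potassium.

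**The case against.** The strongest reply is that Section 3.3.1 is a summary and Section 6 is the rule, so the likelier fault is one sentence that is too strong. The same table row supports this: its rationale column advises caution, not exclusion, for the same potassium groups. Its mitigation cell also advises caution in patients with serious cardiovascular disease after saying they are excluded. Changing the sentence to a caution would remove the contradiction for both potassium groups with no eligibility change. This stands as an open possibility. The mitigations come from a risk management plan that the documents do not reproduce, so they do not settle which text reflects the sponsor's intent. Either way the protocol describes a safeguard that its criteria do not contain.

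A second point is that the three-to-two split looks sharper than it is. Serious cardiovascular disease and thyrotoxicosis reach exclusion only through exclusion 6, with the same requirement that the disease be uncontrolled and the same reliance on judgement. That is fair. The count shows which groups are named by class; it does not measure a safety gap.

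Third, Section 7.10 sends sites to the prescribing information and the Medical Monitor when in doubt. The SAP also reports important protocol deviations separately (Table 1.14 and Listing 8), so the eligibility summary is not the only reporting route. Both points soften the consequence, but neither supplies the exclusion.

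**Conclusion.** The concern holds. Section 3.3.1 states an exclusion that the eligibility criteria do not apply. Two of its five stated groups have only partial, discretionary cover through exclusion 6.

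The practical weight is small. The number of affected participants cannot be derived from the documents. The added risk is limited because inclusion 9 requires 3 months of prior ICS/LABA. All arms receive the same drug, so no arm comparison, power figure or primary analysis changes. Confidence is high on the mismatch between the sections. The point about SAP Section 4.1 depends on an assumed eCRF layout, and the tension with Section 7.9 depends on what predisposed means. This is a minor safety-text correction that should be made at the next amendment.

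**What to change.** Add to Section 6.2 an exclusion for known uncorrected hypokalaemia, taken from medical history or existing records at Visit 1, with no new test.

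Then make the wording on predisposition in Section 3.3.1 agree with what Sections 6.2 and 7.9 apply. Either define the group, say whether it includes users of non-potassium-sparing diuretics, and add it to Section 6.2; or reword Section 3.3.1 so that it no longer claims an exclusion for that group. The direction is for the sponsor to choose, since it holds the risk management plan.

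The cost is one criterion, one aligned sentence and a few more screen failures. The analysis does not change. Because the criterion relies on history and records, it will catch only hypokalaemia that is already known.

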### 3.3.2. Overall Benefit: Risk Conclusion

GlaxoSmithKline (GSK) has assessed this study for any potential risks that a subject may experience. The investigational product (IP) FF/VI will be used as is detailed in the prescribing information and has an acceptable safety profile for clinical use and there are no significant associated risks. This conclusion is supported by the results of previously performed clinical studies with the products in healthy volunteers and subjects with Asthma and COPD and post-marketing experience (see local label).

There is a small risk of destabilising asthma when switching to Relvar/Breo. Patients will be provided with rescue medication and will be educated to recognise symptoms of asthma worsening and instructed to contact the HCP in this event.

Taking into account the measures taken to minimize risk to subjects participating in this study, the potential risks identified, associated with FF/VI are justified by the anticipated benefits that may be afforded to patients with asthma.

More detailed information about the known and expected benefits and risks and reasonably expected adverse events of Relvar/Breo ICS/LABA may be found in the IB, Summary of Product Characteristics and Subject Information Leaflet.

## 4. OBJECTIVES AND ENDPOINTS

Objectives	Endpoints
Primary	
To compare the effect of 6 months use of the CIS on adherence to ELLIPTA maintenance therapy when both the subject and the HCP are supplied with data from the maintenance sensor versus no data supplied to the subject and HCP (Arm 1 vs Arm 5)	Percentage of ELLIPTA doses taken (daily adherence  ) between the beginning of month 4 and the end of month 6 as determined by the maintenance sensor

Objectives	Endpoints
Secondary	

To compare the effect of 6 months use of the CIS on adherence to ELLIPTA maintenance therapy for the following aspects of the CIS:
 
 
• Maintenance data only supplied to subjects versus no data supplied to the subject (Arm 2 vs Arm 5)
 
• Rescue and Maintenance data supplied to subject and HCP versus no data supplied to the subject and HCP (Arm 3 vs Arm 5)
 
• Rescue and Maintenance data only supplied to subject versus no data supplied to the subject (Arm 4 vs Arm 5)
 
	
 
• Percentage of ELLIPTA doses taken (daily adherence) between the beginning of month 4 and the end of month 6 as determined by the maintenance sensor
 

To compare the effect of the CIS on adherence to ELLIPTA maintenance therapy of the individual CIS treatment arms versus no data supplied to the subject and HCP.
	
 
• Percentage of ELLIPTA doses taken (daily adherence) between the beginning of month 1 and the end of month 3
 
• Percentage of ELLIPTA doses taken (daily adherence) between the beginning of month 1 and the end of month 6
 

To evaluate the effect of 6 months use of the CIS on a subject's rescue medicine usage
	
 
• Percentage of rescue free days measured between the beginning of month 4 and the end of month 6 as determined by the rescue sensor records of date, time, and number of inhaler actuations.
 
• Total rescue use measured between the beginning of month 4 and the end of month 6 as determined by the rescue sensor records of date, time, and number of inhaler actuations.
 


To evaluate the effect of 6 months use with the CIS on a subject's asthma control
	
 
• Change from baseline (Randomisation) in ACT total score at Month 6, measured at baseline (Visit 2, 3 or 4) and Month 6 (Visit10)
 
• Percentage of patients becoming controlled as defined as an Asthma Control Test score <math>\geq 20</math> at Month 6 (Visit 10)
 
• Percentage of patients with an increase from baseline <math>\geq 3</math> in ACT total score at Month 6 (Visit 10)
 
• Composite endpoint - Percentage of patients who have either an ACT total score of <math>\geq 20</math> or an increase from baseline of <math>\geq 3</math> in ACT total score at Month 6 (Visit 10)
 

Objectives	Endpoints
Exploratory and Other Objectives	

To evaluate the effect of 6 months use of the CIS on adherence to ELLIPTA maintenance therapy on the following aspects of the CIS:
 
 
• HCP having access to sensor data
 
• Rescue Medication data being available
 
	
 
• Percentage of ELLIPTA doses taken (daily adherence) between the beginning of month 4 and the end of month 6 as determined by the maintenance sensor
 

To evaluate the effect of 6 months use with CIS on health care utilisation
	
Health care utilisation endpoints will include the following and will be collected from a subject's medical records.
 
 
• Number of outpatient visits relating to asthma
 
• Number of primary care visits relating to study HCP dashboard review (for relevant study arms)
 
• Number of and duration of hospitalisations, and ER visits due to asthma
 
• Annualised rate of severe exacerbations
 
• Number of unscheduled visits to primary care related to Asthma
 


To evaluate the effect of 6 months use with CIS on the following patient reported outcomes (PROs):
 
 
• Asthma Symptom Utility Index (ASUI)
 
• St Georges Respiratory Questionnaire (SGRQ)
 
• Patient Activation Measure (PAM)
 
• Medication Adherence Report Scale for Asthma (MARS-A)
 
• Beliefs in Medicine Questionnaire (BMQ).
 
	
 
• Percentage of patients meeting a responder threshold of <math>\geq 0.09</math> points improvement (increase) from baseline (Randomisation) for the ASUI total score at Month 6
 
• Percentage of patients meeting a responder threshold of <math>\geq 4</math> points improvement from baseline (Randomisation) for the SGRQ total score at Month 6
 
• Mean change from baseline (Screening) in PAM total score at Month 6
 
• Mean change from baseline (Screening) in MARS-A total score at Month 6
 
• Mean change from baseline (Screening) at Month 6 in BMQ: 
 
○ General Benefit score
 
○ General Harm score
 
 
 

[figure not shown]
Objectives	Endpoints
	
 
○ General Overuse score
 
○ Specific Necessity score
 
○ Specific Concern score
 

To assess the reliability and usability of the CIS	
 
● Incidence of Medical Device Incidents between the beginning of Month 1 and the end of Month 6.
 

To explore impact of adherence on the biomarker Fractional exhaled Nitric Oxide (FeNO)	FeNO at Screening (Visit 1), Randomisation (Visit 2,3 or 4), Month 1 (Visit 5) and Month 6 (Visit 10).
To explore impact of adherence on the physiological marker Peak Expiratory Flow (PEF)	
 
● PEF at Screening (Visit 1), Randomisation (Visit 2,3 or 4), Month 1 (Visit 5) and Month 6 (Visit 10).
 
● Change from baseline (Visit 2, 3 or 4) in PEF measured at Month 1 (Visit 5) and Month 6 (Visit 10)
 

To characterize patient experience of the CIS for subjects	
 
● Exit Questionnaires at Month 6 (Visit 10)
 
● Exit Interviews for a sub set of subjects at Month 6 (Visit 10)
 

Safety Objectives	Safety Endpoints
To evaluate the incidence of SAEs, Non-Serious Adverse Events that lead to withdrawal from study and Non-serious Adverse Drug Reactions in asthmatic subjects using the CIS	
 
● SAEs, Non-Serious Adverse Events that lead to withdrawal and Non-serious Adverse Drug Reactions
 

1. Daily adherence is defined as the subject taking one dose of Relvar/Breo ELLIPTA, within a 24 hour period, starting at 12.00am each day.

